Blood for Anti-Drug (pembrolizumab) Antibodies ^s				X ^s	X ^s			X ^s			X ^s	X ^s	
Blood for Genetics ^u				X									
Blood for plasma for Correlative Studies ^v				X						X			
Blood for serum for Correlative Studies ^v				X						X			
Blood for DNA for Correlative Studies ^w				X	X	X				X			
Blood for RNA for Correlative Studies ^w				X	X	X				X			
Blood for MDSC Assays ^w				X	X	X				X			
Efficacy Measurements													
Tumor Imaging			X ^x					X ^y		X ^y	X ^z		X ^b
Brain Imaging			X ^x										
Tumor Tissue Collection													
Newly Obtained (required) and Archival (if available) Tissue Collection for biomarker analysis ^{aa}	X ^{aa}												X ^{bb}

- a. In general, assessments/procedures are to be performed on Day 1 and prior to the first dose of treatment for each cycle unless otherwise specified
- b. In subjects who discontinue study therapy without documented disease progression, every effort should be made to continue monitoring their disease status by tumor imaging every 9 weeks (± 7 days) in the first year and every 12 weeks (84 ± 7 days) after year 1 until (1) the start of new anti-cancer treatment, (2) disease progression as assessed by the investigator/site radiologist, (3) death, or (4) the end of the study, whichever occurs first.
- c. After the start of new anti-cancer treatment or documented disease progression as assessed by the Investigator/local radiologist, the subject should be contacted by telephone approximately every 12 weeks to assess for survival status. Updated survival status may be requested by the Sponsor at any time during the course of the study. Upon Sponsor notification, all subjects who do not/will not have a scheduled study visit or study contact during the Sponsor defined time period will be contacted for their survival status (excluding subjects that have a death event previously recorded).
- d. In general, the window for each visit is ± 3 days unless otherwise noted. Study personnel will access IVRS/IWRS to obtain randomization number and study drug assignment. Cycle 1 treatment must be given within 3 days of randomization number assignment in IVRS/IWRS.

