7.1.2.6 Tumor Imaging and Assessment of Disease

The process for image collection and transmission to the central imaging vendor can be found in the SIM. Tumor imaging may be performed by computed tomography (CT-chest, abdomen, pelvis) (strongly preferred) or magnetic resonance imaging (MRI), but **the same imaging technique should be used in a subject throughout the trial.**

Bone scans will also be utilized to assess osseous metastases. Additionally, plain X-ray evaluation will be obtained for symptomatic sites with negative bone scan evaluations. If clinically indicated, sites may also obtain MRI or FDG-PET if it is part of the institutional standards to evaluate baseline bone metastasis. If considered positive per site interpretation, they should be sent to the central imaging vendor, in addition to the bone scan.

A central imaging vendor using RECIST 1.1 will be used to determine subject eligibility.

The central imaging vendor will receive all scheduled images at the timepoints specified in the Study Flow Chart from the sites as well as any unscheduled imaging data. All tumor

imaging, including confirmatory tumor imaging, should be submitted to the central imaging vendor for evaluation and should be submitted in a timely fashion.

The Sponsor will also receive results for a retrospective analysis of treatment response/progression to be performed by the central imaging vendor, using RECIST 1.1/irRECIST. Imaging data will be documented in the Sponsor data collector on the appropriate electronic case report forms (eCRFs).

Treatment decisions will be based on the site's assessment of tumor response and progression.

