7.1.2.6.2 On Study Tumor Imaging

The first post treatment tumor imaging assessment should be performed at 9 weeks (63 days \pm 7 days) from the date of allocation. Thereafter, subsequent tumor imaging should be performed every 9 weeks (63 days \pm 7 days) or more frequently, if clinically indicated. After 12 months, imaging frequency should be reduced to every 12 weeks (84 \pm 7 days). Imaging should follow calendar days and not be delayed for any dose interruptions that may occur.

Per RECIST 1.1, partial or complete response should be confirmed by a repeat tumor imaging not less than 4 weeks from the date the response was first documented. The tumor imaging for confirmation of response may be performed at the earliest 4 weeks after the first indication of response, or at the next scheduled tumor imaging, whichever is clinically indicated.

Imaging should continue to be performed until disease progression, the start of new anti-cancer treatment, withdrawal of consent, death, or notification by the SPONSOR, whichever occurs first. Disease progression may be confirmed at least 4 weeks after the first tumor imaging indicating progressive disease in clinically stable subjects.

Subjects who have unconfirmed disease progression may continue on treatment until progression is confirmed (or possibly even later) provided they have met the conditions detailed in Section 7.1.2.6.5.

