7.1.2.6.4 RECIST 1.1

RECIST 1.1 will be applied by the central imaging vendor retrospectively as the primary measure for assessment of tumor response. All tumor imaging should be submitted to the central imaging vendor.

7.1.2.6.5 irRECIST

irRECIST is RECIST 1.1 adapted as described below to account for the unique tumor response seen with immuno-therapeutics.

irRECIST will be used by site investigators and local radiology review to assess tumor response and progression, and make treatment decisions. This data will be collected in the clinical database.

irRECIST will be used by the central imaging vendor, however, this evaluation will be done retrospectively.

irRECIST takes into account the clinical condition/stability of subjects, as described in [Table 6](#), in addition to response or progression via tumor imaging

Clinically stable is defined by the following criteria:

- Absence of symptoms and signs indicating clinically significant progression of disease, including worsening of laboratory values
- No decline in ECOG performance status
- Absence of rapid progression of disease
- Absence of progressive tumor at critical anatomical sites (e.g., cord compression) requiring urgent alternative medical intervention

Table 6 irRECIST: Tumor Imaging and Treatment after 1st Radiologic Evidence of PD or SD, CR or PR

	Clinically Stable		Clinically Unstable	
	Tumor Imaging	Treatment	Tumor Imaging	Treatment
1 st radiologic evidence of PD	Repeat tumor imaging at ≥ 4 weeks at site to confirm PD	May continue study treatment at the site Investigator's discretion while awaiting confirmatory scan by site	Repeat tumor imaging at ≥ 4 weeks to confirm PD by the site investigator/local radiology review	Discontinue treatment
Repeat tumor imaging confirms PD	No additional tumor imaging required	Discontinue treatment (exception is possible upon consultation with Sponsor).	No additional tumor imaging required	N/A
Repeat tumor imaging shows SD, PR or CR	Continue regularly scheduled tumor imaging assessments	Continue study treatment at the site Investigator's discretion	Continue regularly scheduled tumor imaging assessments	May restart study treatment if condition has improved and/or clinically stable per site Investigator's discretion. Next tumor imaging should occur according to the every 9 week (63 \pm 7 days) imaging schedule in the first year or every 12 weeks after one year.

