8.2.3.1 Efficacy Endpoints

The primary efficacy endpoint is objective response rate (ORR), defined as the proportion of subjects in the analysis population who have complete response (CR) or partial response (PR), based on RECIST 1.1 by the central imaging vendor at any time during the study. As supportive analyses, ORR will also be evaluated by a) site investigator and local radiology review based on RECIST 1.1 and b) irRECIST by the central imaging vendor.

Secondary efficacy endpoints include:

- Duration of response (DOR), defined as the time from first documented evidence of CR or PR until disease progression or death due to any cause, whichever occurs first, for subjects who demonstrate CR or PR, based on RECIST 1.1 by the central imaging vendor.
- Disease control rate (DCR), defined as the percentage of subjects who have achieved confirmed CR or PR or have demonstrated SD for at least 24 weeks prior to any evidence of progression, based on RECIST 1.1 by the central imaging vendor.
- Progression-free survival (PFS), defined as the time from first dose of study medication to the first documented disease progression or death due to any cause, whichever comes first, based on RECIST 1.1 by the central imaging vendor.

- Overall survival (OS), defined as the time from first dose of study medication to death due to any cause.

As exploratory endpoints, DOR and DCR and PFS will also be evaluated based on a) RECIST 1.1 by study site and local radiology review and b) irRECIST by the central imaging vendor.

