8.2.5 Statistical Methods

8.2.5.1 Statistical Methods for Efficacy Analyses

Efficacy of pembrolizumab as 2L+ monotherapy for mTNBC will be evaluated primarily in PD-L1 (+) and overall population (all comers) in Cohort A, and also in subjects with PD-L1 strong (+) tumors from Cohorts A and C combined. Cohort A will be evaluated for association between PD-L1 biomarker expression and antitumor activity. A separate biomarker SAP will be devoted to association between PD-L1 biomarker expression and antitumor activity analysis.

The primary efficacy endpoints are ORR based on RECIST 1.1 by the central imaging vendor in subjects with PD-L1 (+) mTNBC of Cohorts A, overall population (all comers) of Cohort A and in subjects with PD-L1 strong (+) mTNBC. The point estimate 95% Agresti-Coull (A-C) confidence interval (CI) (as determined by the upper and lower 97.5% one-sided confidence bounds) will be provided based on normal approximation for the binomial distribution. Subjects without response data will be counted as non-responders.

Similarly, a supportive analysis to the primary method, ORR based on RECIST 1.1 by study site investigator and local radiology review will also be performed in the same fashion.

For the secondary endpoint of DCR, similar estimation methods used for ORR will be applied.

For DOR, PFS and OS, Kaplan-Meier (KM) curves, median estimates, and survival at 6 and 12 months based on the KM curves (95% CI is based on Greenwood's formula) will be provided as appropriate. Subjects without efficacy evaluation data or without survival data will be censored at Day 1. The restricted mean survival time (RMST) for DOR will also be provided as a supportive analysis.

Censoring rules for DOR are summarized in [Table 9](#).

Table 9 Censoring Rules for DOR

Situation	Date of progression or censoring	Outcome
No progression nor death, no new anti-cancer therapy initiated	Last adequate assessment	Censor (non-event)
No progression nor death, new anti-cancer therapy initiated	Last adequate assessment before new anti-cancer therapy initiated	Censor (non-event)
≥ 2 consecutive missed adequate disease assessments	Last adequate assessment prior to ≥ 2 missed adequate disease assessments	Censor (non-event)
Death or progression after ≤ 1 missed adequate disease assessments	Death or progression	End of response (Event)

A missed disease assessment includes any assessment that is not obtained or is considered inadequate for evaluation of response.

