Similar estimation methods will be applied to the efficacy analyses for the subjects with PD-L1 (+) mTNBC in Cohort B.

[Table 10](#) summarizes the key efficacy analyses for primary and secondary endpoints in this study.

Table 10 Analysis Strategy for Primary/Secondary Efficacy Endpoints in Cohorts A and C

Endpoint/Variable (Description, Time Point)	Statistical Method	Analysis Population	Missing Data Approach
Primary:			
ORR, based on RECIST1.1 by the central imaging vendor	95% Agresti-Coull CI	ASaT - PD-L1 (+) - overall - PD-L1 strong (+)	Subjects with missing data are considered non-responders
Secondary:			
Response duration (DOR) Based on RECIST1.1 
 o by the central imaging vendor o by study site investigator and local radiology review 	Summary statistics using Kaplan-Meier method	All responders - PD-L1 (+) - overall - PD-L1 strong (+)	Non-responders are excluded in analysis
ORR Based on RECIST1.1 
 o by study site investigator and local radiology review 	Agresti-Coull 95% CI	ASaT - PD-L1 (+) - overall - PD-L1 strong (+)	Subjects with missing data are considered non-responders
DCR Based on RECIST1.1 
 o by the central imaging vendor o by study site investigator and local radiology review 	Agresti-Coull 95% CI	ASaT - PD-L1 (+) - overall - PD-L1 strong (+)	Subjects with missing data are considered non-responders
Progression-free survival (PFS) Based on RECIST1.1 
 o by the central imaging vendor o by study site investigator and local radiology review 	Summary statistics using Kaplan-Meier method	ASaT - PD-L1 (+) - overall - PD-L1 strong (+)	Censored at last assessment
Overall survival (OS)	Summary statistics using Kaplan-Meier method	ASaT - PD-L1 (+) - overall - PD-L1 strong (+)	Censored at last assessment
95% confidence interval is determined by the upper and lower 97.5% one-sided confidence bounds.			

Similar efficacy methods will be applied to Cohort B for subjects with PD-L1 (+) tumors receiving pembrolizumab as 1L monotherapy for mTNBC.

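### Central-review PFS and DOR censor subjects who stop imaging at site-assessed progression or start new therapy without central progression; this probably biases both upward, and the planned site-review analyses only partly show by how much

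*Combined protocol and SAP*

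**What the plan says.** **Endpoints.** Protocol 3.2 lists DOR and PFS by central RECIST 1.1 as key secondary objectives for the 2L+ populations. Section 8.2.3.1 has PFS "defined as the time from first dose of study medication to the first documented disease progression or death due to any cause", on the central read. DOR ends likewise at progression or death.

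**Who reads, and when.** Section 7.1.2.6.4: "RECIST 1.1 will be applied by the central imaging vendor retrospectively as the primary measure for assessment of tumor response". Section 7.1.2.6: "Treatment decisions will be based on the site's assessment of tumor response and progression".

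**When imaging stops.** Section 7.1.2.6.2: "Imaging should continue to be performed until disease progression", new anticancer treatment or another listed event. It does not name the assessor. Footnote b of the 6.1 flow chart, for subjects who stop therapy without documented progression, does: "disease progression as assessed by the investigator/site radiologist". Footnote c and 7.1.5.3.4 then move subjects to telephone follow-up for survival.

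**Censoring.** For DOR without progression or death, Table 9 censors at the last adequate assessment. If new therapy was started, the date is "Last adequate assessment before new anti-cancer therapy initiated". Table 9 also censors after two or more consecutive missed assessments. For PFS the only rules are the Table 10 entry, "Censored at last assessment", and a sentence censoring subjects without evaluation data at Day 1. The sSAP (Tables 1 and 2) is essentially the same.

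**Site-review analyses.** Sections 4.2.3.1 and 8.2.3.1, Table 10 and sSAP Table 2 plan efficacy by RECIST 1.1 per site and local radiology review, including PFS and DOR. Section 8.2.3.1 calls site DOR and PFS exploratory, while Table 10 lists them as secondary.

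**The concern.** The event is defined by one reader, and the observation window is closed by another. Because the central read comes later, nothing keeps a subject in imaging once the site has called progression and moved on. If the central reader does not call progression on the available scans, the subject leaves the risk set at the last scan.

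Kaplan-Meier estimation treats that exit as unrelated to prognosis. Here that is doubtful: a physician has just judged the disease to be progressing or has changed treatment. If such subjects would soon have had central progression, removing them as non-events raises the curve.

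This matters because the trial is single-arm and estimation-only. Durability of response carries much of the interpretation of an ORR, and DOR rests on few subjects. The Table 11 planning scenarios have 24 responders of 160, 16 of 93 and 11 of 55. If all 11 PD-L1 strong (+) responders progressed, 20% discordance would affect about 0.20 × 11 = 2.2 of them.

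**Working it through.** **No planned figure to reproduce.** The documents give no event count, precision target or site-central discordance rate for PFS or DOR. The check is of the rules first, then of a plausible size.

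**Step 1: one subject through the rules.** Take site progression without central progression.
- PFS: no central event, so censored at the last assessment unless a death is counted.
- DOR, if a central responder: censored at the last adequate assessment, or at the last one before new therapy.
- Later death: an event for DOR only if at most one assessment was missed. For PFS, death is an event by definition, but the rule for death after missed scans or new therapy is not stated.
- Site PFS: an event, in the same treated population.
- Site DOR: an event only if the site also called a response, since the analysis covers responders by the reader concerned.
- New therapy with no progression by either reader: Table 9 censors it for DOR, and no planned PFS or DOR analysis is stated to count it.

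**Step 2: illustrative size for PFS.** Inputs:
- Scans every 9 weeks in year 1 (7.1.2.6.2). Those at weeks 9 and 18 precede 6 months (26.1 weeks).
- Latent median of 2.7 months, about 11.7 weeks, borrowed from the second-line TNBC subgroup in protocol Table 1; exponential times assumed.
- Discordance *d* of 10, 20 or 30%: assumed.
- No deaths and no confirmatory scans: assumed.

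The chance of site progression at each scan is h = 1 − 2^(−9/11.7) = 0.413. With site progression as the event, S = (1 − h)² = 0.587² = 34.4%. With discordant cases censored at that scan, S = [1 − (1 − d)h]².

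| d | Factor per scan | 6-month PFS, discordant censored | Excess over 34.4% |
|---|---|---|---|
| 10% | 0.628 | 39.4% | 5.0 points |
| 20% | 0.669 | 44.8% | 10.4 points |
| 30% | 0.711 | 50.5% | 16.1 points |

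A simulation on the protocol's scan schedule agreed: 39, 45 and 51%, against about 34%. When half of the discordant cases had a scan 4 weeks later that central review called progression, it gave 36, 39 and 41%, against 34–35%.

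**Step 3: the median.** It can fall only on a scan date. The curve first reaches 50% or less at week 18 for d = 0, 10 and 20% (34.4, 39.4 and 44.8%). At d = 30% it is 50.5% at week 18, so the median moves to week 27.

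**Step 4: DOR at 12 months.** Same method, with five scans (weeks 9 to 45) before 52.2 weeks, counted for simplicity from first response. Both latent medians are assumed.
- 26 weeks: h = 1 − 2^(−9/26) = 0.213. Site progression as event: 0.787⁵ = 30.1%. Censored: 34.4, 39.2 and 44.5%.
- 52 weeks: h = 1 − 2^(−9/52) = 0.113. Site progression as event: 54.9%. Censored: 58.5, 62.3 and 66.2%.

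The shift is upward in every case.

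**The case against.** **Site-review analyses exist.** A reader might infer that no planned analysis counts these subjects as events. The documents do not support that: site-review PFS and DOR are planned in both the protocol and the sSAP, and site progression is an event there. What remains is narrower. Site review changes the reader at every time point, site DOR drops central responders who were not site responders, and new therapy is not stated to count anywhere.

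**Site criteria.** Because 7.1.2.6.5 has sites use irRECIST for treatment decisions, a reader might infer that the site analyses rest on irRECIST calls. The plan specifies RECIST 1.1 for them.

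**Further scans.** Clinically stable subjects are to have a repeat scan at least 4 weeks after first progression (Table 6), and "imaging, including confirmatory tumor imaging, should be submitted to the central imaging vendor for evaluation". Site confirmation also makes it likelier that central progression comes first. Footnote b covers only subjects who stopped therapy without documented progression. This stands and reduces discordance, but does not remove it. Section 7.1.2.6.2 makes confirmation optional. The text of 7.1.2.6.5 excuses clinically unstable subjects from a repeat scan while Table 6 lists one; those two passages need reconciling.

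**Deaths.** Survival follow-up continues, so some of these subjects become PFS events at death. This also stands, but only in part for DOR, because Table 9 censors after two or more missed assessments.

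**Median inflation.** A reader might scale the median by 1/(1 − d). That assumes continuous observation; on a 9-week grid the median can stay put or jump a whole interval, as step 3 shows.

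**Need.** The trial tests no hypotheses, and censoring before new therapy is an explicit rule. Both are true, and neither shows how far the estimates depend on that rule.

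**Conclusion.** The point holds in a limited form. Central-review PFS and DOR censor subjects with site progression or new therapy but no central progression or death. That censoring is probably informative and biases both upward. Site-review PFS largely exposes the effect of discordant progression calls; site DOR does so less well, and neither is stated to address new therapy.

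The size cannot be fixed from the documents. In the illustration, 6-month PFS is overstated by about 5 to 16 points at 10 to 30% discordance without confirmatory scans, and by about 2 to 7 points if half of the discordant cases have one read as progression. Both ranges ignore deaths. For 12-month DOR the excess is about 4 to 14 points, depending on the assumed median. ORR is not affected. This is a worthwhile, inexpensive addition, and the planned main analysis need not change.

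**What to change.** In protocol 8.2.5.1 and Table 10, and in sSAP 3.6.1 and Table 2:

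1. Add a PFS censoring table like the one for DOR. It should cover new anticancer therapy, missed assessments, and death after either.
2. Pre-specify one sensitivity analysis for central PFS and one for central DOR, the latter in central responders. Site-assessed progression, or start of new anticancer therapy, without prior central progression counts as an event on its own date.
3. Report the number censored by reason, separating site progression without central progression from new therapy.

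While editing, settle whether site-review DOR and PFS are exploratory or secondary.

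The cost is two extra Kaplan-Meier summaries and a table of counts. Site assessments and subsequent therapy are already collected, so no scans are added. The new estimates may be less favourable. They should be labelled a conservative bound, because they count site calls that the central reader did not accept and treat every new therapy as progression.

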6.2 Second Course Phase (Retreatment)

Trial Period:	Treatment Cycles ^a						End of Treatment	Post-Treatment		
Treatment Cycle/Title:	1	2	3	4	To be repeated beyond 6 cycles		Discon	Safety Follow-up	Follow Up Visits ^b	Survival Follow-up ^c
					5	6				
Scheduling Window (Days) ^d :		± 3	± 3	± 3	± 3	± 3	At time of discon	30 days post discon	Every 9 weeks post discon	Every 12 weeks
Administrative Procedures										
Eligibility Criteria ^e	X									
Concomitant Medication Review ^f	X	X	X	X	X	X	X	X		
Clinical Procedures/Assessments										
Review Adverse Events	X	X	X	X	X	X	X	X ^g	X ^g	
Full Physical Examination	X						X			
Directed Physical Examination		X	X	X	X ^h	X	X			
Vital Signs and Weight ⁱ	X	X	X	X	X	X	X	X		
ECOG Performance Status	X	X	X	X	X	X	X	X		
Pembrolizumab Administration ^j	X	X	X	X	X	X				
Post-study Anticancer Therapy Status									X	X
Survival Status ^c	<----->									X
Laboratory Procedures/Assessments: Analysis performed by LOCAL laboratory										
Pregnancy Test – Urine or Serum β-HCG ^k	X									
PT/INR and aPTT	X ^l									
Complete Blood Count (CBC) with Differential ^m	X ^l	X	X	X	X	X	X	X ⁿ		
Chemistry Panel ^m	X ^l	X	X	X	X	X	X	X ⁿ		
Urinalysis	X									
T3, FT4 and TSH ^m	X ^l		X		X ^h			X ⁿ		
Efficacy Measurements										
Tumor Imaging ^o	X				X		X ^p		X	

- a. In general, assessments/procedures are to be performed on Day 1 and prior to the first dose of treatment for each cycle unless otherwise specified. Treatment cycles are 3 weeks.
- b. In subjects who discontinue study therapy without documented disease progression, every effort should be made to continue monitoring their disease status by tumor imaging every 9 weeks (63 ± 7 days) in the first year and every 12 weeks (84 ± 7 days) after year 1 until (1) the start of new anti-cancer treatment, (2) disease progression as assessed by the investigator/site radiologist, (3) death, or (4) the end of the study, whichever occurs first.
- c. After the start of new anti-cancer treatment or documented disease progression as assessed by the Investigator/local radiologist, the subject should be contacted by telephone approximately every 12 weeks to assess for survival status. Updated survival status may be requested by the Sponsor at any time during the course of the study. Upon Sponsor notification, all subjects who do not/will not have a scheduled study visit or study contact during the Sponsor defined time period will be contacted for their survival status (excluding subjects that have a death event previously recorded).
- d. In general, the window for each visit is ± 3 days unless otherwise noted.
- e. Subjects who either a) attain a CR and discontinue treatment or b) discontinue treatment after 24 months on pembrolizumab for reasons other than disease progression or intolerability may restart trial treatment if they meet the criteria specified in Section 7.1.5.2.1.
- f. Concomitant medications – Enter new medications started during the trial through the Safety Follow-up visit. Record all medications taken for SAEs as defined in Section 7.2.
- g. Record all AEs occurring within 30 days after the last dose of trial treatment. Report all SAEs (related and unrelated to trial treatment) and ECIs occurring up until 90 days after the end of treatment or 30 days after the end of treatment if the subject initiates new anticancer therapy, whichever is earlier. Afterwards, report only SAEs and ECIs that are related to trial treatment.
- h. To be repeated every 2 cycles after Cycle 5.
- i. Vital signs to include temperature, pulse, respiratory rate, weight and blood pressure.
- j. Pembrolizumab is given as a 200 mg dose on the first day of each 3 week cycle. Subjects who restart treatment should resume at the same dose and cycle interval which they were receiving prior to discontinuation.
- k. For women of reproductive potential, a urine or serum pregnancy test should be performed within 72 hours prior to first dose of trial retreatment. If the urine test is positive or cannot be confirmed as negative, a serum pregnancy test will be required. Pregnancy tests (serum and/or urine tests) should be repeated if required by local guidelines.
- l. Laboratory tests for determining eligibility for retreatment are to be performed within 10 days prior to the first retreatment dose of pembrolizumab. See Section 7.1.3 for details regarding laboratory tests.
- m. After Cycle 1, lab samples can be collected up to 72 hours prior to the scheduled time point. Blood draws for thyroid function tests should be done prior to dosing at the scheduled timepoint, however results can be reviewed after dosing. See Section 7.1.3 for details regarding laboratory tests.
- n. Unresolved labs that are drug related AEs should be followed until resolution. Labs do not need to be repeated after the end of trial treatment if labs are within normal range.
- o. Tumor imaging must be performed within 28 days prior to restarting treatment with pembrolizumab. Tumor imaging should continue to be performed every 9 weeks (63 ± 7 days) after the date of allocation or more frequently if clinically indicated in the first year. After 12 months, imaging frequency should be reduced to every 12 weeks (84 ± 7 days). Tumor imaging timing should follow calendar days and should not be adjusted for any dose modifications. The same image modality acquisition and technical parameters should be used throughout the study.
- p. In subjects who discontinue study therapy without confirmed disease progression, tumor imaging should be performed at the time of treatment discontinuation (i.e., date of discontinuation ± 4 week window). If previous tumor imaging was obtained within 4 weeks prior to the date of discontinuation, then tumor imaging at treatment discontinuation is not required.

